CALLiNGS Protocol: Care Across Locations Longitudinally of Goals and Symptoms

NCT : pending

June 23, 2018

Junior Faculty Career Development Award

**CALLiNGS Protocol: Care Across Locations Longitudinally in Navigation of Goals and Symptoms
Interdisciplinary Pediatric Telepalliative Consultations for Hospice Teams**

Project Abstract

Despite 35+ pediatric hospice discharges to rural providers each year in Nebraska; primary care providers, hospice directors, and hospice nurses in Nebraska report they feel unprepared to manage pediatric hospice patients. In this pilot intervention study guided by the Theory of Unpleasant Symptoms, web conferencing services will connect an inpatient pediatric palliative care team with adult outpatient hospice providers to support local providers in assessing pediatric-specific care needs and implementing developmentally-appropriate pediatric treatment plans for 10-20 medically-complex children. The objective of this CALLiNGS (Care Across Locations Longitudinally in Navigation of Goals and Symptoms) mixed-methods study is to test feasibility, acceptability, and quality of life outcomes from using web-conferencing technology to connect a hospital-based interdisciplinary pediatric palliative care with statewide field-based hospice teams during interdisciplinary meetings at a minimum of every 15 calendar days. The reason for selection of every 15 days is because Medicaid requires that interdisciplinary hospice teams meet at a minimum of every 15 days to review patient symptom burden, medications, and plan of care. The study team hypothesizes that telepalliative care for children has the potential to improve the quality of care delivered to pediatric palliative care patients in a rural state by facilitating the confidence and comfort of local providers, enhancing goals of care conversations, improving symptom management for patients and therefore quality of life for family members, and creating a unified and cross-setting shared care model. The study intends to determine whether direct patient-specific pediatric mentorship or general pediatric palliative education is more helpful for hospice staff, for patient symptoms, and for family quality of life. If feasible this model could transform the pediatric palliative care delivery in the state of Nebraska with expanded opportunity for application in settings with similar subspecialty provider shortages.

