Expected Outcomes Based on geography and shortage of pediatric palliative subspecialists in Nebraska, the current model of hospice services is one in which pediatric patients are managed by local adult-based hospice teams after discharge from the pediatric hospital (34 such in the past 16 months). Sixty percent of academic pediatricians in Nebraska who served as primary providers for consecutive pediatric home discharge patients self-reported feeling “very deficient” to “deficient” when asked about competence after supporting terminal patients and families in care at home (n=12).¹ The knowledge gap and discomfort in managing children with complex symptom burden is magnified further for family practice or internal medicine teams serving in hospice roles for children in rural communities. Through a new telepalliative technology platform, this study fosters collaboration and communication to improve the quality of care for pediatric patients receiving hospice care in rural states. This model implements human interaction through technology to challenge the existing paradigm of silo-based care of pediatric palliative care patients. With roll-out of this intervention, we anticipate increase in pediatric hospice utilization (decreased in-hospital deaths). If feasible this model could transform the pediatric hospice care delivery in the state of Nebraska with expanded opportunity for application in settings with similar subspecialty provider shortages.

Table 1. Aims, Measures, and Time Points for this Exploratory Pilot Feasibility Study		
Aim	Completed by	Measures and Designated Timepoints
Investigate symptom burden for pediatric patients and the quality of life impact for pediatric patients and their families	Patient Parent	PROMIS-37 – Every 15 days, as child is able Proxy-PROMIS-37 and PedsQL Family Impact completed by Proxy – Every 15 days
Evaluate the self-efficacy (comfort), knowledge, and self-perceived adequacy of local hospice providers	Hospice Nurse Team	Pediatric Palliative Care Questionnaire – Enrollment and end of study Qualitative Debriefing Survey (2 qualitative questions) – End of study
Explore the acceptability of teleconferencing services as a form of pediatric palliative care consultation	Hospice Nurse Team	Technology Acceptance Model (TAM) Tool – After telehealth encounters

Research Plan

Background and Significance

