Description – This mixed-methods pilot feasibility study includes use of web-conferencing technology to connect a hospital-based interdisciplinary pediatric palliative care with statewide field-based adult hospice teams. The first collaborative meeting includes a comprehensive pediatric palliative care needs assessment completed with the patient, family, the pediatric palliative care team, and the local hospice team to include goals of care in symptom, relational, psychological, and spiritual domains as well as advance care planning content.⁴¹ The ongoing intervention with the hospice team includes either pediatric educational modules OR shared visits during interdisciplinary meetings (with the invitation to the patient and family for inclusion via tele-presence) at a minimum of 60-min every 15 calendar days.

Team-Approach – The study is specifically an interdisciplinary team empowerment design. The telepalliative team “interacts with the goal of transferring knowledge from one discipline to another; which allows members to inform each other’s work and compare findings”⁴² toward shared, collective outcomes.

Sample and inclusion criteria – The study population includes all patients ages birth to 18 years referred to the inpatient pediatric palliative care team at Children’s Hospital Omaha or the University of Nebraska Medical Center during hospitalization who are enrolling on home hospice services within the state of Nebraska at time of discharge from the hospital. Based on a chart review of three consecutive years (2013-2016), this situation includes an average of 30 pediatric patients per year. The mean age of this patient population based on three-year data is 7.4 years (range 3 days to 18 years); primary diagnosis included genetic (27%), oncology (23%), cardiac (18%), neurologic (18%), pulmonary (14%). Family distance from the hospital averaged 110 miles (range 7 to 320 miles). These children are noted to have a significant symptom burden to include pain, dyspnea, fatigue, nausea, and anxiety/depression.

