- **Consent/Enrollment** - Consent and enrollment procedures will follow strict Institutional Review Board expectations and ethical standard.
- **Stakeholder Survey** – Local hospice team will be asked about their perceived self-efficacy (comfort), knowledge, and perceived adequacy in caring for pediatric children in using quantified Pediatric Palliative Care Questionnaire scale pre- and post-child enrollment.

- *Symptom Burden and Quality of Life* – Child, guardian, and hospice team nurse will complete Pediatric PROMIS-37™ every 15 days to assess for symptom burden and translated quality of life.
- *Interdisciplinary (IDT) Telepalliative Care Meetings* –Technology Acceptance Model survey will occur every 15 days (in the pediatric palliative educational arm and in the patient-specific case discussion arm) as an automatic screen on the closing telepalliative screen to evaluate acceptability of technology interface. The reason for this frequency is that Medicaid requires that hospice interdisciplinary team interactions occur at a minimum of every 15 days.
- *Team Debriefing* – At enrollment and at the conclusion of the study period (six months per enrollee with total project duration 2 years) or within 3 days following a child’s natural end of life; the local hospice team members will be invited to engage in a qualitative interview with two thematic topics: 1. Please describe your experience caring for a pediatric patient and 2. Please describe your experience with telepalliative use. This interview will be recorded and coded for content using Atlas.ti software.

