Data Plan – Descriptive statistics will be computed for each outcome variable at each time point. Repeated measures ANOVA and trend plots will be used to explore quantified symptom burden and quality of life trends over time. The association between individual and multiple symptoms will be explored via linear and multiple linear regression. Bland-Altman plots will be used to assess concordance between symptom and quality of life reporting. Crude (unadjusted) associations between demographics (such as family economics, diagnosis, level of technology, delay to initial palliative care) and symptoms / quality of life will be explored via ANOVA or linear regression, as appropriate. A similar analysis will be used to explore the association between how hospice team self-perceived confidence and knowledge of pediatric palliative care and child symptom and quality of life. In the event the assumptions of the parametric tests identified above are violated, the appropriate non-parametric test will be used. When a non-parametric test is used, the median and interquartile range for continuous outcomes will be reported. A significance level of 0.05 will be used to judge statistical significance. In addition to monitoring for statistical significance, the study team will follow minimally clinically important

difference (MCID) for symptom burden or quality of life values over time.⁵⁸ MCID has been defined as “the smallest difference in a score of a domain of interest that patients perceive to be beneficial and that would mandate, in the absence of troublesome side effects and excessive costs, a change in the patient's management.”⁵⁹ Content of the two qualitative interview questions will be analyzed thematically using a qualitative coding methodology in Atlas.ti ([name] has completed graduate level qualitative coursework >9 credit hours and published >4 qualitative method manuscripts).⁶⁰

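### The abstract sets out to determine which of two arms helps more, but no analysis in the Data Plan compares the arms

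*Combined protocol and SAP*

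**What the plan says.** The Project Abstract poses a comparative question: "The study intends to determine whether direct patient-specific pediatric mentorship or general pediatric palliative education is more helpful for hospice staff". The same sentence adds patient symptoms and family quality of life, so there are two approaches and three outcome groups.

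The design carries the comparison into delivery. Research Design and Methods, Description: "The ongoing intervention with the hospice team includes either pediatric educational modules OR shared visits during interdisciplinary meetings". In the step-by-step outline, the technology acceptance survey is to run every 15 days "in the pediatric palliative educational arm and in the patient-specific case discussion arm".

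The Data Plan opens with "Descriptive statistics will be computed for each outcome variable at each time point" and continues with "Repeated measures ANOVA and trend plots will be used to explore quantified symptom burden and quality of life trends over time". It then lists regressions among symptoms, Bland-Altman plots for concordance, crude associations with demographics, associations between hospice-team confidence and knowledge and the child's outcomes, non-parametric fallbacks, a 0.05 significance level, tracking against a minimally important difference, and thematic coding of interviews.

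The Specific Aims are not comparative: Aim 1 investigates symptoms and quality of life under the service, Aim 2 is before-and-after, and Aim 3 explores acceptability.

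**The concern.** A question about which of two approaches is more helpful needs a contrast between them. A trend over time in all children together mixes the two arms with the course of the illness and cannot separate one arm from the other. As written, the plan therefore does not say how the abstract's own question will be answered.

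If a comparison is added after data collection, the score, the reporter, the time contrast and the model will all be open to choice once results are visible. Those choices are real. PROMIS covers several symptoms. Table 1 lists patient and parent as its reporters, while Study Variables and Measures and the step-by-step outline add the hospice nurse. Child self-report is planned "Every 15 days, as child is able", in a population whose ages run from 3 days to 18 years. With a 0.05 threshold already in the Data Plan, an unplanned contrast that happened to cross it could be read as the answer.

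**Working it through.** **Step 1: set the question against the analyses.** The plan states no figure on this point, so the check is textual.

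- *Descriptive statistics*: by outcome and time point; arm not mentioned.
- *Repeated measures ANOVA and trend plots*: trends over time; no group factor and no arm-by-time term.
- *Symptom regressions and Bland-Altman plots*: relations among symptoms and agreement between reports; these would not normally carry an arm term.
- *Crude associations*: the covariates are demographics. The list is open-ended, but intervention arm is not a demographic.
- *Hospice-team confidence and knowledge*: related to child outcomes, not compared between arms.
- *Minimally important difference and thematic coding*: no split by arm.

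None of the three outcome groups in the abstract has an analysis that uses arm.

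**Step 2: what an arm contrast could show.** Inputs from the documents: 10-20 children (Project Abstract), or 10-20 patients per hospice (Selection methods and sample size). The second reading allows a larger total; for instance, one hospice of 20 in each arm gives 20 per arm. Assumptions, none stated in the documents: 1:1 allocation, one continuous score per child, no clustering by hospice, no dropout.

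Half-width of the 95% confidence interval for the difference in means, in SD units, with n per arm: t(0.975, 2n − 2) × √(2/n).

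- n = 5: 2.306 × 0.632 = 1.46 SD
- n = 10: 2.101 × 0.447 = 0.94 SD
- n = 20: 2.024 × 0.316 = 0.64 SD

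Repeated assessments could narrow these intervals for symptoms and family quality of life. The gain depends on the within-child correlation and on how many assessments each child completes, which the documents do not give, so no figure is offered. The number of hospice staff is not given either, so there is no figure for the staff outcome.

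**Step 3: the unit that receives the intervention.** Both arms are delivered to hospice teams. The half-widths above treat children as independent. If each arm is one hospice, which is the example used for n = 20, the interval reflects variation between children only, and any difference between the two hospices is part of the apparent arm effect.

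**The case against.** The strongest reply is that this is labelled an exploratory pilot feasibility study. Its main objective in the abstract concerns feasibility, acceptability and quality of life, and all three aims and Table 1 are non-comparative. On that view one sentence in the abstract is out of line, and rewording it would be enough. Part of this stands: the sample is openly not sized on power, so low precision is not itself a fault, and rewording would remove the sharpest contradiction. It would still leave a two-arm study with no plan to show results by arm.

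A second reply is that a split by arm is obvious and would be done anyway. The Data Plan does not exclude it. But nothing commits to it, and the score, reporter and time contrast would still be unnamed.

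Two stronger readings are tempting and should not be drawn:

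- A reader might infer that the arms have no allocation method. The running text gives neither a method nor the number of hospices, but the figures could not be read here, and one stands beside the description of the case-discussion arm. Absence of an allocation scheme cannot be asserted.
- A reader might infer that any comparison would be hopelessly imprecise. The 1.46 and 0.94 SD figures belong to the smaller reading of the sample size; the per-hospice wording permits 20 per arm or more, and repeated measures would help. The documents do not fix the precision.

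**Conclusion.** The point holds and should be fixed. The abstract asks which of two approaches is more helpful for three outcome groups, the design has two arms, and the Data Plan contains no analysis that uses arm. This conclusion rests on running text alone and needs no assumption.

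The half-widths of 1.46, 0.94 and 0.64 SD are illustration only, under the assumptions in the working. They support one further conclusion: at the sizes illustrated, the study can offer an estimate with an openly wide interval, and *determine* is too strong a verb. Whether even that estimate can be credited to the arm depends on how many hospices contribute to each arm, which the readable text does not say.

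**What to change.** In the Data Plan, show descriptive statistics and trend plots by arm, and add an exploratory between-arm estimate with 95% confidence interval for each outcome group:

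1. *Patient symptoms*: PROMIS symptom domain scores, from a mixed model with arm, time, arm-by-time and a random effect for child. Before the data are seen, name the time contrast (for example, change from first assessment to a stated occasion) and the main reporter. Guardian proxy is one reasonable choice, because not every child can self-report; child and nurse reports would be shown alongside. Reconcile Table 1 with the text on whether the nurse completes PROMIS.
2. *Family quality of life*: PedsQL Family Impact total score, with the same model and a named time contrast.
3. *Hospice staff*: arm difference in change on the instrument scheduled in Table 1 as "Pediatric Palliative Care Questionnaire – Enrollment and end of study".

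Include hospice in the models where several hospices contribute to each arm. If there are only one or very few per arm, state that arm and hospice effects cannot be separated and report the arm results descriptively. State the number of children per arm, which also means reconciling the abstract's 10-20 children with the later per-hospice figure.

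In the Project Abstract, change *determine* to *explore*.

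The cost is one word in the abstract, a few sentences in the Data Plan and a few more models on data already collected. The downsides are a visibly wide interval and a hospice term that may not be estimable.

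### The first child and family symptom and quality-of-life score is not tied to enrolment or to a time before the first telehealth session, so a pre-telehealth value is not guaranteed

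*Combined protocol and SAP*

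**What the plan says.** All references are to the combined protocol and SAP.

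- **Child and family scores.** Table 1 gives the child's own PROMIS-37 as "Every 15 days, as child is able" and the parent measures as "Proxy-PROMIS-37 and PedsQL Family Impact completed by Proxy – Every 15 days". The step-by-step outline adds the nurse as a respondent and gives the same interval: "Child, guardian, and hospice team nurse will complete Pediatric PROMIS-37™ every 15 days to assess for symptom burden". None of these entries gives a start day.
- **Staff measures.** Table 1 does give a start for staff: "Pediatric Palliative Care Questionnaire – Enrollment and end of study". The step-by-step outline also places the team debriefing at enrolment and at the end.
- **Baseline form.** The step-by-step outline has a baseline demographics and needs assessment at the first visit, described as current standard of care. PROMIS-37 and PedsQL are not listed in it.
- **Sessions.** Under Research Design and Methods (Description), "The first collaborative meeting includes a comprehensive pediatric palliative care needs assessment". The ongoing intervention, either educational modules or shared visits, then runs at least every 15 calendar days.
- **Analysis.** The Data Plan states: "Repeated measures ANOVA and trend plots will be used to explore quantified symptom burden and quality of life trends over time". It also follows minimally clinically important differences (MCID) over time and relates staff confidence and knowledge to child symptoms and quality of life. It defines no time zero, no baseline covariate and no rule for deaths or missing forms.

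**The concern.** Aim 1 and the central hypothesis are about symptom burden and quality of life under telepalliative care. The Project Abstract also asks whether patient-specific mentorship or general education helps more. Both questions need a score taken before the study sessions can have acted.

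Forms and sessions share one 15-day interval, and only the staff measures have a stated start. A team following the text could therefore take the first child and family score before, at or after the first session, or at day 15, and could do so differently from family to family. Change before the first form would then go unseen. An MCID would be counted from an undefined point. Children aged from birth to 18 years with varied diagnoses could differ in starting severity between arms, with no common starting score to adjust for. A late first form also removes some children from any analysis of change. A missed pre-session score cannot be recovered later.

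**Working it through.** The plan has no power or precision figure to reproduce; the 10-20 children are a feasibility number. The check is of the schedule, followed by a sensitivity range.

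**1. Start day.** Every place that gives timing for PROMIS-37 or PedsQL Family Impact (two entries in Table 1, one in the step-by-step outline) gives an interval only. Enrolment is named for the staff questionnaire and the debriefing. Both readings below are open.

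**2. Forms per child.** Follow-up is at most six months, taken as 180 days, and 180/15 = 12 intervals.
- First form at day 0: 12 + 1 = 13 possible forms; a change score needs follow-up to day 15.
- First form at day 15: 12 possible forms; a change score needs follow-up to day 30.

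**3. Children without a change score.** The documents give no survival figure. Assume exponential time to death or exit with median m, so that P(exit before t) = 1 − 2^(−t/m). For m = 60: 1 − 2^(−15/60) = 0.159 and 1 − 2^(−30/60) = 0.293, a difference of 0.134. That is 2.7 of 20 or 1.3 of 10.

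| Assumed median (days) | Exit before day 15 | Exit before day 30 | Exit in days 15-30 | Of 20 | Of 10 |
|---|---|---|---|---|---|
| 30 | 0.293 | 0.500 | 0.207 | 4.1 | 2.1 |
| 60 | 0.159 | 0.293 | 0.134 | 2.7 | 1.3 |
| 90 | 0.109 | 0.206 | 0.097 | 1.9 | 1.0 |
| 180 | 0.056 | 0.109 | 0.053 | 1.1 | 0.5 |

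Only the days 15-30 columns depend on the start day. Exits before day 15 are lost to a change score under either schedule.

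**4. Change missed before day 15.** This applies if the first session is near day 0 and the first form is at day 15. With linear change the share missed is 15/180 = 8.3%. With front-loaded change of half-life h (assumed), it is (1 − 0.5^(15/h)) / (1 − 0.5^(180/h)): 18% for h = 60 days, 30% for h = 30 and 50% for h = 15.

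**5. Who enters the planned analysis.** Classical repeated measures ANOVA uses complete series. The share still followed at day 180 is 2^(−180/m): 1.6%, 12.5%, 25% and 50% for medians of 30, 60, 90 and 180 days, or 0.3, 2.5, 5 and 10 of 20 children. An enrolment form alone would not bring short series into that analysis.

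**The case against.** The text is silent on the start day; it does not rule out day 0. The step-by-step outline lists consent, the staff survey and the symptom scores before the telehealth meetings, which fits a first score before the first session. Figures are missing from the available text, so a schedule shown only there cannot be checked. This stands: a reader might infer that no enrolment form is planned, and the documents do not say that. But list order is not a stated time, and the plan names enrolment where it wants it.

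A reader might also take the first collaborative meeting as the start of the intervention. The documents do not support this firmly. The needs assessment is called standard of care, and the ongoing intervention is described separately as modules or shared visits. A score at that meeting could be pre-intervention.

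Nor would an enrolment score be an untreated value. Eligible children have been referred to the inpatient palliative team and are enrolling on home hospice. The score would be pre-telehealth and would coincide with the move home.

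The counts in the working rest on assumed survival and on a day-15 first form. If the first form is in practice near day 0, the gain in children with a change score is about nil. The Data Plan specifies no between-arm comparison, so baseline adjustment applies only once one is written. Finally, this is an exploratory pilot that disclaims power. That limits the severity, but a pilot should still settle when its first score is taken.

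**Conclusion.** The point holds as a gap in the schedule: a common pre-telehealth score is not secured for the Aim 1 trends, the MCID tracking or the mentorship-versus-education question. It is a cheap improvement worth making, not a flaw that invalidates the pilot.

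The certain part needs no assumption: the start day is unstated and may vary between families. The sizes are conditional. If the first form falls at day 15, and exit is exponential with a median of 30 to 180 days, about 1 to 4 of 20 children (0.5 to 2 of 10) lose a change score that a day-0 form would have given. The share of change missed runs from 8% if linear to 50% under the steepest assumed front-loading.

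A reader might infer that the schedule is to blame for all early deaths giving no change score. It is not: it affects only exits between days 15 and 30.

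**What to change.** 1. In Table 1 and the step-by-step outline, for child, guardian and nurse PROMIS-37 and for PedsQL Family Impact, replace the interval with: *at enrolment, before the first study telehealth session (module or case discussion), then every 15 days*. Keep the allowance for children who cannot self-report.
2. In the Data Plan, define the enrolment score as time zero for trends and as the reference for MCID tracking. Use it as a baseline covariate in any between-arm comparison and in the staff-confidence analysis.
3. Replace repeated measures ANOVA with a mixed model that uses all available scores, so that children with short series contribute. Report the number of forms, deaths and exits at each time point.

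Cost: one extra set of existing forms per family and nurse, and a few lines of text. The burden falls around the hospital-to-home transition, and the nurse may then know the child only slightly. The change does not recover children who leave before day 15, and the write-up should call the value pre-telehealth. If an enrolment form is already intended, item 1 only puts that in writing.

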Selection methods and sample size – Pediatric patients and their families will be informed of the CALLINGS Protocol (Care Across Locations Longitudinally in Navigating Goals and Symptoms) at time of home hospice enrollment to foster consecutive sampling enrollment. The local nurse team hospice will receive telehealth interdisciplinary team meetings specific to patient need for up to 60 minutes every 15 days. The pilot study size of 10-20 patients per hospice is grounded in evidence-base for feasibility study sample population size rather than power scales.⁴³ Note that study duration would be for a maximum of six months per enrollee (due to hospice enrollment being a six-month commitment as standard).

- Pediatric patient-specific case discussions for enrolled pediatric patients at hospice staff interdisciplinary team meeting every 15 days for 60 min sessions via telehealth

[figure not shown]
home hospice enrollment to foster consecutive sampling enrollment. The local nurse team hospice will receive telehealth interdisciplinary team meetings specific to patient need for up to 60 minutes every 15 days. The pilot study size of 10-20 patients per hospice is grounded in evidence-base for feasibility study sample population size rather than power scales.⁴³ Note that study duration would be for a maximum of six months per enrollee (due to hospice enrollment being a six-month commitment as standard).

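### At 10-20 children per hospice the plan's own volumes give roughly one to three hospices per arm, too few to determine which form of support is more helpful, and the sample size is stated two ways

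*Combined protocol and SAP*

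**What the plan says.** The Project Abstract sets a comparative goal: "The study intends to determine whether direct patient-specific pediatric mentorship or general pediatric palliative education is more helpful for hospice staff", and extends it to patient symptoms and family quality of life. Research Design and Methods (Description) places delivery with the team: "The ongoing intervention with the hospice team includes either pediatric educational modules OR shared visits during interdisciplinary meetings". The step-by-step outline (Interdisciplinary Telepalliative Care Meetings) treats the two forms as arms: "in the pediatric palliative educational arm and in the patient-specific case discussion arm".

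The size is given twice. Selection methods and sample size says "The pilot study size of 10-20 patients per hospice is grounded in evidence-base", and adds that the basis is evidence "for feasibility study sample population size rather than power scales". The abstract speaks of "developmentally-appropriate pediatric treatment plans for 10-20 medically-complex children", with no reference to the number of hospices.

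No readable text gives the number of hospices, how arms are assigned, or whether a hospice stays in one arm. A figure in the sample size section could not be read. The Data Plan sets a 0.05 significance level but names neither an arm comparison nor a hospice term.

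**The concern.** When support is delivered to a team, the team is the natural unit of comparison. Children cared for by one hospice share its nurses, skill, staffing, case mix and location. If a hospice stays in one form of support, the evidence about the forms comes from the number of hospices, and extra children within a hospice add little. Concentrating 10-20 children in each hospice therefore works against the comparison. With one hospice per arm, the better-looking form could simply be the one given to the better-placed hospice, and no later analysis could separate the two.

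If one team receives both forms, at once or in turn, the difficulty changes. The same nurses take what they learned under one form into the other, and transfer of knowledge is the mechanism the Team-Approach paragraph relies on.

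**Working it through.** The plan has no power calculation to reproduce. The check asks how many hospices its own volumes can fill, and what that number can show.

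**Inputs**
- Eligible children: Sample and inclusion criteria says "this situation includes an average of 30 pediatric patients per year". Expected Outcomes gives 34 in 16 months, and 34 × 12/16 = 25.5 a year.
- Time: Team Debriefing gives "six months per enrollee with total project duration 2 years". The enrolment window is 18 months if every child can have six months of follow-up, and 24 months at the outside.
- Children per hospice: 10 to 20.
- Uptake: not given. Full uptake is the most favourable case.

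**Hospices that can be filled** = yearly rate × years ÷ children per hospice
- 18 months: 25.5 × 1.5 = 38 and 30 × 1.5 = 45 children. 38/20 = 1.9 and 45/10 = 4.5 hospices.
- 24 months: 25.5 × 2 = 51 and 30 × 2 = 60 children. 51/20 = 2.6 and 60/10 = 6 hospices.
- Overall about 2-6 hospices, or roughly 1-3 per arm. Three per arm needs every eligible child for the full 24 months at only 10 per hospice.
- At 50% uptake (assumed) and 30 a year: 22.5 to 30 children, so 22.5/20 = 1.1 to 30/10 = 3 hospices, or 0.6-1.5 per arm.
- The abstract also mentions 35 or more discharges a year to rural providers. At 35, the most favourable case is 35 × 2/10 = 7 hospices, still short of four per arm.
- If 10-20 were both the study total and the number per hospice, there would be at most 20/10 = 2 hospices, one per arm.

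**What k hospices per arm can show, if each stays in one arm**

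Between-hospice degrees of freedom = 2(k − 1). Smallest two-sided permutation p = 2/C(2k, k), capped at 1.

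| k per arm | df | smallest p |
|---|---|---|
| 1 | 0 | 1 |
| 2 | 2 | 2/6 = 0.33 |
| 3 | 4 | 2/20 = 0.10 |
| 4 | 6 | 2/70 = 0.029 |

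A t-test on hospice means can reach 0.05 at k = 2 or 3, but only for very large differences. The difference detectable with 80% power is ncp × √(2(1 + (m − 1)ICC)/(mk)), with m children per hospice and ncp (found by simulation) 5.65 at k = 2 and 3.76 at k = 3. For m = 10-20 and assumed ICC 0.01-0.10, that is about 1.4-2.5 SD at k = 2 and 0.75-1.3 SD at k = 3.

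**A child-level test that ignores hospice (hypothetical)**

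With one hospice per arm and no true effect, type I error = 2 × P(t > t_crit/√((1 + (m − 1)ICC)/(1 − ICC))), df = 2m − 2. Simulation agrees.

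| m | ICC 0.01 | ICC 0.05 | ICC 0.10 |
|---|---|---|---|
| 10 | 0.06 | 0.11 | 0.17 |
| 20 | 0.07 | 0.17 | 0.27 |

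The ICCs are assumed, because the documents give none.

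**The case against.** The strongest reply is that this is an exploratory pilot that disclaims power. None of the three Specific Aims is a contrast between arms, and the Data Plan names no such test. That stands. It confines the point to the comparative statement in the abstract and makes the type I figures hypothetical: they show what a child-level arm test would do, not a fault in an analysis the plan specifies.

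Second, a reader might infer that arm is fixed by hospice and that confounding follows under any allocation rule. The documents do not support this. Team-level delivery makes it likely, but the figure could not be read, and hospices receiving both forms in sequence cannot be excluded. Each hospice would then be its own control, and the problem would be carry-over.

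Third, the hospice count follows only from the sample size section. If the abstract's 10-20 children are the study total, drawn from teams across the state, many hospices could each contribute one or two children. That is a fair reading, and it is why the two statements must be reconciled.

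Fourth, a reader might infer that a target of 10-20 per hospice steers the study towards high-volume hospices. The plan sets no volume threshold and intends consecutive enrolment of eligible children, so that is speculation.

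Finally, the plan expects referrals to rise. It gives no size for the rise. Four hospices per arm at 10 each would need 8 × 10 = 80 enrolled children, or 40 a year for 24 months at full uptake.

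**Conclusion.** The concern holds conditionally. Under the per-hospice wording, the plan's volumes allow roughly one to three hospices per arm. If each hospice stays in one arm, arm and hospice are inseparable at one per arm. At two or three, separation is possible in principle but has very little power, and a permutation test of hospices cannot reach 0.05. It would be too strong to say that an arm difference can never be told from a hospice difference; that is strictly true only at one per arm. If hospices receive both forms, carry-over replaces confounding.

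On any reading, the two sample sizes conflict, and the number of hospices and the level of allocation are not stated in readable text. The stated intent to determine which form is more helpful is not supported as the plan stands. The feasibility and acceptability aims are unaffected. This should be fixed, but it does not stand in the way of the pilot. The count rests on full uptake and an 18-24 month window; the power and type I figures rest on assumed ICCs.

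**What to change.** - State one total number of children, reconciling the Project Abstract with the sample size section, and state the number of hospices.
- Fix the arm for each hospice team before its first child enrols, by random draw if the figure in the sample size section does not already set an allocation.
- In the Data Plan, specify that any arm contrast is analysed on hospice-level summaries.
- With fewer than four hospices per arm, report the arms side by side without a test, and change the abstract's stated intent from determining which form is more helpful to describing the two. Four per arm is only the point at which a permutation test can go below 0.05 (0.029, at the most extreme split); it does not ensure useful power.

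The cost is protocol wording, a random draw and, if more hospices take part, more letters of agreement. The comparative claim becomes weaker. If the total is set at 10-20, there are fewer children per team (10/8 = 1.25 to 20/8 = 2.5 with four hospices per arm). There may also be fewer children overall, since two hospices under the per-hospice wording already imply 2 × 10 = 20 to 2 × 20 = 40.
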